- Over 60% of HPV-positive HNSCC express PD-L1, and tumor infiltration by PD-1+CD8+ T cells is frequently present in HPV-positive HNSCC.
- Anti-PD-1 mAb can be safely administered with high dose cisplatin.
- PD-1 blockade has demonstrated synergistic activity with radiotherapy in vivo.
- PD-1 blockade can reverse T cell exhaustion to chronic viral infections such as HPV and therefore, may be particularly effective in viral-induced tumors.
- ISA101b vaccination has demonstrated clinical and immunologic responses in HPV-16+ cancers.

2. STUDY OBJECTIVES

Primary Hypothesis and Endpoints

The addition of pembrolizumab and HPV-16 E6/E7 specific therapeutic vaccination (ISA101b) to cisplatin-based chemoradiotherapy will improve PFS for patients with newly diagnosed, local-regionally advanced, intermediate risk HPV-associated HNSCC.

2.1

Primary

The primary objective of this study is to evaluate treatment intensification using fixed-dose pembrolizumab (concurrent) plus ISA101b added to the standard, concurrent cisplatin-IMRT in patients with PULA HPV-16+, “intermediate risk” HNSCC in order to recommend survival estimates in a subsequent definitive randomized trial as determined by the endpoint of 2-year PFS rate (please see Section 10.2 for Statistical Methods).

2.2

Secondary

Secondary objectives for this study include:

- To evaluate the toxicity of the combination of pembrolizumab and ISA101b and concurrent cisplatin-IMRT in patients with PULA HPV-16+ “intermediate risk” HNSCC

2.3 Exploratory

- To evaluate associations between tumor PD-L1 expression and PFS and OS in patients treated with pembrolizumab and ISA101b; PD-L1 status will not be used during this trial for treatment decisions
- To evaluate the safety, feasibility and patient compliance with continued administration of single agent pembrolizumab 200 mg IV q21 days for 14 further doses after completion of chemoradiation with concomitant pembrolizumab
- To evaluate associations between HPV E6/E7 seroreactivity and PFS in p16-positive patients treated with and without pembrolizumab and therapeutic ISA101b
- To evaluate the frequency and functional phenotype of HPV-16 E6 and E7 specific circulating activated, PD-1+ T cells in patients treated with and without pembrolizumab
- To evaluate the dynamics of PD-L1 expression in the tumor and TILs via a repeat biopsy after 2-3 weeks after pembrolizumab and ISA101b vaccination in patients with accessible tumor.
- To evaluate the tumor microenvironment, activation, and proliferation markers on TIL and NK cells in pre- and post-treatment specimens, including CD3, CD8, CD45RO, CD4/FOXP3, PD-L1, and Ki-67
- To evaluate the dynamic expression of TA-specific T cells in serial peripheral blood mononuclear cells (PBMCs) by flow cytometry

3.

PATIENT SELECTION

3.1

Inclusion Criteria

Each patient must meet all of the following inclusion criteria to be enrolled in the study:

- Patients must have histologically-confirmed head and neck squamous cell carcinoma with no evidence of distant metastasis. The primary site will be the oropharynx. Patients with squamous cell carcinoma of unknown primary, metastatic to cervical lymph nodes, are permitted to enroll provided all other eligibility criteria are met.
- Patients must have intermediate risk disease, defined below. Staging evaluation should be determined by imaging studies and complete head and neck exam in accordance with the American Joint committee on Cancer Staging Manual, 7th edition.
 - Patients must meet one of the following criteria:
 - Oropharynx: p16(+) PLUS HPV ISH(+) AND one of the following
 - T3 OR \geq N2a AND \geq 10 pack-years tobacco exposure (see Tobacco Assessment Form, Appendix A)
 - T4 or N2c/N3 disease irrespective of tobacco exposure
 - Unknown primary: p16(+) PLUS HPV ISH(+) AND one of the following
 - \geq N2a AND \geq 10 pack-years tobacco exposure

- N2c/N3 disease irrespective of tobacco exposure

Note: for patients with oropharyngeal or unknown primary tumors, p16 status must be known, and HPV-16 ISH should also be performed. p16-positive disease is defined as $\geq 70\%$ of tumor cells demonstrating diffuse nuclear and cytoplasmic staining by p16 immunohistochemistry (IHC).

- Patients should be considered not a candidate for curative-intent surgery with diagnosis of AJCC 7th edition Stage III, IVa, or IVb disease. Diagnostic excisional biopsy of primary tumor and/or nodal sites is permitted.
 - Diagnostic simple palatine or lingual tonsillectomy is permitted, provided patient has RECIST-measurable nodal disease.
 - Patients with a second HNSCC primary tumor are eligible for this study, provided more than 2 years have elapsed since the first diagnosis of HNSCC, the original tumor was managed with surgery only (no adjuvant chemotherapy or radiotherapy), and has not recurred.
 - Patients with simultaneous primaries are excluded, with the exception of patients with bilateral tonsil/base of tongue HPV+ cancers or patients with T1-2, N0, M0 differentiated thyroid carcinoma (resected or management deferred), who are eligible.
 - No prior systemic (chemotherapy or biologic/molecular targeted therapy) or radiation treatment for head and neck cancer.
 - Patients may have received chemotherapy or radiation for a previous, curatively treated non-HNSCC malignancy, provided at least 2 years have elapsed.
 - Patients must be untreated with radiation above the clavicles.
 - Patients with a history of curatively-treated non-HNSCC malignancy must be disease-free for at least 2 years except for excised and cured: carcinoma-in-situ of breast or cervix; non-melanoma skin cancer; T1-2, N0, M0 resected differentiated thyroid carcinoma; superficial bladder cancer; T1a or T1b prostate cancer comprising $< 5\%$ of resected tissue with normal prostate specific antigen (PSA) since resection.
 - The patient must undergo a MANDATORY research biopsy at baseline. There will be 2 other optional biopsies that the patient will be asked to consent to, the first is during week 2 of pembrolizumab/ISA101b vaccination, prior to start of cisplatin-IMRT (this correlates to week -1), the second one will be during week 2 after the start of IMRT (this correlates to week 1). All patients will be evaluated for the feasibility of research biopsy at the time of enrollment, as a condition of eligibility. The performing physician must agree that a cup forceps biopsy or an 18 to 14 gauge core needle biopsy can be safely performed. Every effort will be made to couple the baseline research biopsy to a standard of care diagnostic or staging procedure.
- NOTE:** Patients who have had research tissue procured under an omnibus tissue consent, who are determined to have sufficient tissue for analysis of immune- inflammatory biomarkers per the study PI, may substitute the archived tissue and do not need to undergo baseline research biopsy. Such tissue must have been obtained within the prior 24 weeks and no interval anti-cancer therapy administered.
- Eastern Cooperative Oncology Group (ECOG) Performance Status 0-1 (See Appendix B)
 - Age ≥ 18
 - Patients must have clinical evidence of disease
 - Patients must demonstrate adequate organ function as defined in Table 1; all screening labs should be performed within 10 days of treatment initiation.

○ Table 1. Adequate Organ Function Laboratory Values

System	Laboratory Value
Hematological	
Absolute neutrophil count (ANC)	$\geq 1,500 / \text{mm}^3$
Platelets	$\geq 100,000 / \text{mm}^3$
Hemoglobin	$\geq 9.0 \text{ g/dL}$

System	Laboratory Value
Renal	
Serum creatinine OR	$\leq 1.5 \times$ upper limit of normal (ULN) OR
Measured or calculated ^a creatinine clearance (GFR can also be used in place of creatinine or CrCl)	
Creatinine clearance ≥ 60 mL/min (for subject with creatinine levels $> 1.5 \times$ institutional ULN) determined by 24-hour collection or estimated by Cockcroft-Gault formula:
 
^a Calculated creatinine clearance = $[(140 - \text{age}) \times (\text{actual body weight in kg}) \times (0.85 \text{ if female})] / (72 \times \text{serum creatinine})$

Hepatic	
Serum total bilirubin	$\leq 1.5 \times$ ULN OR Direct bilirubin \leq ULN for subjects with total bilirubin levels > 1.5 ULN
AST (SGOT) and ALT (SGPT)	$\leq 2.5 \times$ ULN
Coagulation	
International Normalized Ratio (INR) or Prothrombin Time (PT)	$\leq 1.5 \times$ ULN unless subject is receiving anticoagulant therapy as long as PT or PTT is within therapeutic range of intended use of anticoagulants
Activated Partial Thromboplastin Time (aPTT)	$\leq 1.5 \times$ ULN unless subject is receiving anticoagulant therapy as long as PT or PTT is within therapeutic range of intended use of anticoagulants

- Written informed consent must be obtained from all patients prior to study registration. Patients should have the ability to understand and the willingness to sign a written informed consent document.
- If a woman of childbearing potential, documentation of negative pregnancy within 4 weeks prior to first dose (see section 8.1.1). Sexually active patients must agree to use adequate contraceptive measures, while on study and for 120 days after the last dose of study drug. All fertile female subjects (and their partners) must agree to use a highly effective method of contraception. See Appendix E for approved contraceptive methods. Should a woman become pregnant or suspect she is pregnant while in this study, she should inform her treating physician immediately. A negative pregnancy test should be documented during screening and then within 72 hours of first dose.
- Male participants:
A male participant must agree to use a contraception during the treatment period and for at least 120 days after the last dose of study treatment and refrain from donating sperm during this period. See Appendix E for approved contraceptive methods.

3.2

Exclusion Criteria

Patients meeting any of the following exclusion criteria are not to be enrolled in the study:

- Oral Cavity, Larynx, Hypopharynx or Nasopharyngeal primary site
- Current participation in or previous participation in a study of an investigational agent or using an investigational device within 4 weeks of the first dose of study treatment.
- Prior treatment with anti-HPV agents except prevention HPV vaccines
- History of severe allergic or anaphylactic reactions or hypersensitivity to recombinant proteins or excipients in the investigational agents (pembrolizumab and ISA101b (e.g. Montanide and components of reconstitution solution for ISA101b).
- Distant metastatic disease including CNS or leptomeningeal metastases is not allowed.
- Acquired Immune Deficiency Syndrome (AIDS) based upon current CDC definition; note: HIV testing is not required for entry into this protocol. The need to exclude patients with AIDS from this protocol is necessary

because the cisplatin and IMRT involved in this protocol may be significantly immunosuppressive.

- Received prior monoclonal antibody within 4 weeks prior to study Day 1 or who has not recovered (i.e. \leq Grade 1 or at baseline) from adverse events due to agents administered more than 4 weeks earlier.
- Active autoimmune disease requiring systemic treatment within the past 3 months or a documented history of clinically severe autoimmune disease, or a syndrome that requires systemic steroids or immunosuppressive agents. Subjects with vitiligo or resolved childhood asthma/atopy would be an exception to this rule. Subjects that require intermittent use of bronchodilators or local steroid injections would not be excluded from the study. Subjects with hypothyroidism stable on hormone replacement or Sjogren's syndrome will not be excluded from the study.
- Known active Hepatitis B (e.g., HBsAg reactive) or Hepatitis C (e.g., HCV RNA [qualitative] is detected).
- Received prior therapy with an anti-PD-1, anti-PD-L1, anti-PD-L2, anti-CD137, or anti-Cytotoxic T-lymphocyte-associated antigen-4 (CTLA-4) antibody (including ipilimumab or any other antibody or drug specifically targeting T-cell co-stimulation or checkpoint pathways).
- Significant pulmonary disease, including pulmonary hypertension, history of (non-infectious) pneumonitis that required steroids, evidence of interstitial lung disease or active, non-infectious pneumonitis
- History or current evidence of any other medical or psychiatric condition, therapy, or laboratory abnormality that might confound the results of the trial, interfere with the subject's participation for the full duration of the trial, or is not in the best interest of the subject to participate, in the opinion of the treating investigator.
- Peripheral neuropathy \geq Grade 2
- Significant cardiovascular disease, including:
 - Cardiac failure New York Heart Association (NYHA) class III or IV.
 - Myocardial infarction, severe or unstable angina within 6 months prior to Study Day 1.
 - History of serious arrhythmia (i.e., ventricular tachycardia, or ventricular fibrillation).
 - Ventricular cardiac arrhythmias requiring anti-arrhythmic medications.
 - Known left ventricular ejection fraction (LVEF) \leq 50%.
- Significant thrombotic or embolic events within 3 months prior to Study Day 1. Significant thrombotic or embolic events include but are not limited to stroke or transient ischemic attack (TIA). Catheter-related thrombosis is not a cause for exclusion. Diagnosis of deep vein thrombosis or pulmonary embolism is allowed if the patient is clinically stable and has completed or is on stable anti-coagulation therapy.
- Major surgery within 6 weeks prior to Study Day 1 (subjects must have completely recovered from any previous surgery prior to Study Day 1). Biopsy, diagnostic tonsillectomy, airway tumor debulking or excisional lymph node biopsy do not constitute major surgery.
- Active infection requiring antibiotics or antifungals within 7 days prior to first dose of study drug.
- Significant electrolyte imbalance prior to enrollment (note that patients may be supplemented to achieve acceptable electrolyte values):
 - Hypomagnesemia <1.2 mg/dL or 0.5 mmol/L.
 - Hypokalemia < 3.0 mmol/L.
- Women must not be pregnant or breastfeeding because chemotherapy and/or pembrolizumab may be harmful to the fetus or the nursing infant. Pregnant women are excluded from this study because chemotherapy and/or pembrolizumab have the potential for teratogenic or abortifacient effects.
- Live vaccines within 30 days prior to the first dose of trial treatment and while participating in the trial. Examples of live vaccines include, but are not limited to, the following: measles, mumps, rubella, chicken pox, yellow fever, rabies, BCG, and typhoid (oral) vaccine. Seasonal influenza vaccines for injection are generally killed virus vaccines and are allowed; however intranasal influenza vaccines (e.g. Flu-Mist®) are live attenuated vaccines, and are not allowed.
- Has had an allogenic tissue/solid organ transplant.

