Additional analyses conducted by O'Sullivan, et al. (2013) have indicated that patients with p16-positive OPSCC with T4 or N2C-N3 disease have a high-risk of disease progression, even if tobacco exposure is < 10 pack-years. Therefore, these patients are also considered eligible for this clinical trial. The sample size calculations presented in this protocol consider the outcome of all of these eligible patients based on observations from RTOG 0522. It is important to note that many of the clinical trials investigating the impact of tumor HPV status on survival have utilized a validated surrogate; tumor p16-expression status as measured by immunohistochemistry. P16-expression has been shown to have ~92% sensitivity and ~90% specificity in comparison to the gold standard of expression of high-risk HPV oncogenes E6 and E7. For this trial, to ensure enrollment of productive HPV-infected HNSCC patients, we will require both p16 IHC (>70% positive tumor cells) AND HPV DNA measured by ISH or PCR.

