7.2 ISA101b

7.2.1 Study Drug Materials

ISA101b is a vaccine and consists of nine overlapping long E6 peptides (five 32-mer and four 25-mer E6 peptides) and three 35-mer E7 peptides. These peptides overlap by 10 to 18 residues and cover the complete sequence of HPV16 E6 oncoprotein. Most of the E7 oncoprotein sequence is covered by the peptide sequences (only amino acids 57-63 are not covered).

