8.1.1 Required Pre-Registration Evaluations

- History and physical examination, including vital signs, weight, height and ECOG performance status

determination

- Complete blood count, including platelets and differential*
- Blood chemistry studies (may be obtained from whole blood or serum/plasma samples), including BUN, creatinine, electrolytes (K^+ , Na^+ , Cl^- , CO_2), glucose, calcium, Mg^{++} and liver function tests (total protein, albumin, total bilirubin, AST (SGOT), ALT (SGPT), and alkaline phosphatase), uric acid, and lactate dehydrogenase*
- Thyroid function tests, including thyroid stimulating hormone (TSH), free thyroxine, (FT4), anti-thyroglobulin antibody, thyroid peroxidase antibody, thyroid stimulating immunoglobulin, and ANA. Establishing baseline thyroid function and pre-existing thyroid auto-immunity is required, as an appropriate clinical standard prior to chemoradiotherapy for HNSCC as well as anti-PD1 therapy for HNSCC. However, normal thyroid function and absence of subclinical thyroid auto-immunity (example detectable anti-thyroglobulin antibody or detectable thyroid peroxidase antibody) are not eligibility criteria. If subclinical hypothyroidism is detected, treatment should be initiated according to standard practice. If subclinical thyroid auto-immunity is detected, the patient is still eligible.
- For women of child bearing potential: blood pregnancy test within 4 weeks of registration to rule out pregnancy. (Note, pregnancy test will be repeated within 72 hours of initiating protocol treatment.)
- Baseline tumor measurements within 4 weeks prior to registration. Contrasted diagnostic CT scan for staging and baseline tumor measurements. In the rare case that a patient is not a candidate for contrasted diagnostic CT scan (e.g. history of allergic reaction to iodinated contrast despite premedication), MRI of the neck may be conducted for baseline tumor measurements. **Note:** when feasible, a baseline integrated PET/CT with diagnostic contrasted CT scan is preferred. Any scans or x-rays used to document measurable disease should be done as close to study entry as possible and within 4 weeks prior to treatment.
- Evaluation by an otolaryngologist with endoscopy as indicated, within 8 weeks prior to registration. Endoscopy for oropharyngeal carcinoma may be performed as clinically indicated.
- HPV status must be established and positive in accordance with protocol definition
- Tobacco history assessment form (See Appendix A)

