- p. p16 plus HPV ISH status must be established at the participating site, if not previously known before the screening process.
- q. Evaluation by an otolaryngologist with endoscopy may be performed as clinically indicated.
- r. Cisplatin should be administered on Monday, Tuesday, or Wednesday of each treatment week and may be given either before or after the radiation therapy fraction that is given on the same day.
- s. 3 weeks (+/- 1 week) from last dose of Pembrolizumab

*Lab work is to be collected within 10 days prior to Day -14.

15.4 Appendix D: CervISA: Cumulative Summary Tabulation of Treatment Emergent Adverse Events Related to ISA101

With onset date from start vaccination; C2D15

System Organ Class Preferred Term	20µg N=9 n (%)	20µg+INF N=8 n (%)	40µg N=6 n (%)	40µg+INF N=8 n (%)	100µg N=11 n (%)	100µg+INF N=7 n (%)	300µg N=6 n (%)	300µg+INF N=6 n (%)
Any Related Treatment Emergent Adverse Event	4 (44.4)	5 (62.5)	5 (83.3)	6 (75.0)	9 (81.8)	7 (100)	5 (83.3)	6 (100)
Blood and lymphatic system disorders		1 (12.5)		2 (25.0)		1 (14.3)		
Anaemia		1 (12.5)		1 (12.5)		1 (14.3)		
Febrile neutropenia		1 (12.5)		1 (12.5)				
Leukopenia		1 (12.5)						
Neutropenia		1 (12.5)				1 (14.3)		
Thrombocytopenia						1 (14.3)		
Gastrointestinal disorders				1 (12.5)	2 (18.2)			2 (33.3)
Abdominal pain								1 (16.7)
Diarrhoea				1 (12.5)				1 (16.7)
Nausea				1 (12.5)	1 (9.1)			2 (33.3)
Vomiting				2 (18.2)				1 (16.7)
General disorders and administration site conditions	2 (22.2)	3 (37.5)	3 (50.0)	5 (62.5)	8 (72.7)	7 (100)	5 (83.3)	5 (83.3)
Chills						1 (14.3)		
Fatigue				1 (12.5)	1 (9.1)	1 (14.3)	1 (16.7)	3 (50.0)
Influenza like illness		1 (12.5)		2 (25.0)		2 (28.6)	1 (16.7)	1 (16.7)
Infusion site extravasation					1 (9.1)			
Injection site erythema					1 (9.1)	1 (14.3)		
Injection site induration								1 (16.7)
Injection site pruritus	1 (11.1)							
Injection site reaction		1 (12.5)		3 (37.5)	5 (45.5)	4 (57.1)	3 (50.0)	2 (33.3)
Malaise		1 (12.5)			2 (18.2)	1 (14.3)		
Pyrexia	1 (11.1)	2 (25.0)		1 (12.5)	2 (18.2)	2 (28.6)		2 (33.3)
Systemic inflammatory response syndrome							1 (16.7)	
Vaccination site erythema			1 (16.7)					
Vaccination site induration			2 (33.3)		1 (9.1)		1 (16.7)	
Vaccination site nodule						1 (14.3)		
Vaccination site pain						1 (14.3)		
Vaccination site pruritus			1 (16.7)					
Vaccination site reaction		1 (12.5)					1 (16.7)	2 (33.3)
Vaccination site swelling			1 (16.7)	1 (12.5)				
Immune system disorders								2 (33.3)

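### The stated population is HPV-16+, but the inclusion criterion requires only a positive HPV ISH with no genotype, so HPV-16-negative patients can enrol as written

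*Combined protocol and SAP*

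**What the plan says.** Several places fix the population as HPV-16+: the primary objective (section 2.1), the secondary objective (sections 2.2 and 10.1), the opening paragraph of section 10, and the first sentence of section 10.2. The vaccine matches that population. According to section 7.2.1 its peptides "cover the complete sequence of HPV16 E6 oncoprotein" and most of HPV16 E7.

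The text that decides who enters is less specific:

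- Section 3.1, oropharynx: "Oropharynx: p16(+) PLUS HPV ISH(+) AND one of the following".
- Section 3.1, unknown primary: "Unknown primary: p16(+) PLUS HPV ISH(+) AND one of the following".
- Section 3.1, Note covering both tumour groups: "p16 status must be known, and HPV-16 ISH should also be performed".
- Section 1.2: "we will require both p16 IHC (>70% positive tumor cells) AND HPV DNA measured by ISH or PCR".
- Section 8.1.1, screening: "HPV status must be established and positive in accordance with protocol definition".
- Appendix C, footnote p: "p16 plus HPV ISH status must be established at the participating site, if not previously known before the screening process".
- Section 10.1, primary objective: refers to intermediate-risk HPV-positive patients, with no genotype.

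No exclusion criterion in section 3.2 removes tumours caused by another HPV type.

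**The concern.** The population named in the objectives and the population admitted by the criteria are not the same. Under section 3.1 as worded, a p16-positive tumour with a positive HPV ISH qualifies whatever the HPV type. A patient whose tumour is HPV-positive but HPV-16-negative would then receive three vaccinations without the matching target and carry the vaccine's risks, which section 1.6.2 says include systemic allergic reactions.

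That patient would also count in the primary PFS test and in the HPV16 E6/E7 T-cell analyses (sections 2.3 and 9.4.8). If such patients gain less from the regimen, the observed effect is diluted and power falls. Section 10.4 plans no analysis by HPV genotype. Because the HPV-16 test is not mandatory, the genotype of some patients might never be recorded, which would weaken any later attempt to separate them.

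**Working it through.** **Step 1: does any passage close the gap?** Section 3.1 is the binding list, and both of its HPV lines omit the genotype. The Note uses *must* for p16 and *should* for HPV-16 ISH, and asks for no particular HPV-16 result. Section 1.2 asks for HPV DNA without a type, and adds PCR, which section 3.1 does not mention. Section 8.1.1 refers back to the protocol definition, which is section 3.1. Footnote p requires only that status be established. None of these demands an HPV-16-positive result.

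**Step 2: reproduce the planned power.** Inputs from section 10.2: 45 evaluable patients, one-sided alpha 0.10, two-year PFS 65% against 81%, 2 years of accrual plus 1 year of follow-up, exponential test on the hazard estimate.

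- Hazards, -ln(S)/2: λ0 = 0.2154 and λ1 = 0.1054 per year, ratio 0.489.
- Probability of an observed event with uniform accrual: 1 - [exp(-λ) - exp(-3λ)]/(2λ). Times 45, this gives d0 = 15.5 and d1 = 8.5 expected events.
- Power on the log-hazard scale: Φ{[ln(λ0/λ1) - 1.2816/√d0] × √d1} = Φ{[0.715 - 0.325] × 2.912} = Φ(1.135) = 87.2%.

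The stated 87% is reproduced.

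**Step 3: dilution.** The documents give neither the non-16 share q nor the PFS of such patients, so both are assumptions. With non-16 PFS s, the two-year PFS of the mixture is 0.81 - q × (0.81 - s). The formula puts the corresponding single hazard in place of λ1. The simulation draws each patient's own hazard and applies a Wald test to the log hazard (40,000 replicates). Losses are taken against each method's own baseline.

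If non-16 patients stay at the null 65%:

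| Share | Two-year PFS | Formula power (loss) | Simulated power (loss) |
|---|---|---|---|
| 0% | 81.0% | 87.2% | 86.3% |
| 5% | 80.2% | 84.7% (2.5) | 83.0% (3.3) |
| 10% | 79.4% | 81.8% (5.4) | 79.5% (6.8) |
| 15% | 78.6% | 78.6% (8.6) | 75.2% (11.1) |

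If pembrolizumab with chemoradiotherapy brings them to 75%:

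| Share | Two-year PFS | Formula power (loss) | Simulated power (loss) |
|---|---|---|---|
| 0% | 81.0% | 87.2% | 86.2% |
| 5% | 80.7% | 86.3% (0.9) | 85.1% (1.1) |
| 10% | 80.4% | 85.3% (1.9) | 84.1% (2.1) |
| 15% | 80.1% | 84.3% (2.9) | 82.8% (3.4) |
| 20% | 79.8% | 83.3% (3.9) | 81.0% (5.2) |

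The choice of scale matters a little. The hazard-scale formula starts at 86.5%. In the 65% case it gives 82.7%, 78.5% and 73.9% at shares of 5%, 10% and 15%, losses of 3.8, 8.0 and 12.6 points. In the 75% case it gives 80.6% at a 20% share, a loss of 5.9 points.

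**Step 4: sample size.** In the 65% case, keeping 87% power on the log-hazard scale needs 50, 57 or 64 evaluable patients at shares of 5%, 10% or 15%, against the 45 planned from 50 enrolled.

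**Step 5: type I error.** If the regimen does nothing and non-16 patients also have 65% two-year PFS, every patient has the null hazard. The mixture is then the null itself, and the false-positive rate is unchanged.

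**The case against.** The strongest reply is that section 3.1 should be read as a whole. The Note sits directly below the criterion, concerns the same two tumour groups, and names HPV-16 ISH. No pan-HPV assay is named there. On that reading the required positive ISH is the HPV-16 ISH, as the objectives imply. This stands as evidence of intent. A reader might infer from the criterion that the trial chose to admit any HPV type, and the documents do not support that. The reply does not supply the missing requirement, however: no sentence says that the HPV-16 result must be positive, and the Note's verb is weaker than the one it uses for p16.

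A reader might also infer that the study calendar accepts any positive ISH. It does not. The row and footnote p only require that status be established, and the acceptance rule lies in section 3.1.

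The power figures are open to fair challenge. The non-16 share has no source in the documents. The 65% case is the adverse end, because these patients still receive pembrolizumab and chemoradiotherapy. Nor is 81% an HPV-16-specific estimate: section 10.2 obtains it as a 25% relative improvement on 65% (0.65 × 1.25 = 0.8125), and that 65% comes from HPV-positive patients with no genotype stated. These points limit the size of the effect and leave the contradiction in place.

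**Conclusion.** The concern holds as an internal inconsistency. The plan states an HPV-16+ population and uses an HPV16-only vaccine, but its binding criterion, followed exactly, admits HPV-positive, HPV-16-negative patients. The main consequences are unmatched vaccination and an unclear analysis population; loss of power is secondary.

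The size is conditional. For assumed non-16 shares of 5% to 15% the loss is about 2.5 to 9 points by the log-hazard formula and about 3 to 11 by simulation if these patients stay at 65% PFS. If they reach 75%, it is about 1 to 5 points for shares up to 20%. Neither set is a forecast. It would be tempting to conclude that the trial is underpowered or that a positive result would be unreliable. The documents do not support the first, because no share is known and none need arise if sites apply the Note as a requirement. They do not support the second, because type I error is not inflated when these patients sit at the null rate.

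**What to change.** - In section 3.1, for both oropharynx and unknown primary, require a positive HPV-16-specific result before registration, and turn the Note's recommendation to test into a requirement.
- Reconcile the accepted assay, which is ISH in section 3.1 but ISH or PCR in section 1.2, and name it.
- Align sections 1.2 and 8.1.1, the primary objective in section 10.1, the Appendix C row and footnote p.
- If any non-16 patients are already enrolled, keep them in the full analysis set and add a pre-specified HPV-16+ sensitivity analysis. The HPV-16 result must then be recorded for every patient.

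The cost is an amendment to wording, since the Note already calls for the test. The downside is possibly slightly slower accrual.
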